8.6. Safety and Tolerability Assessments

8.6.1. Adverse Events

All AEs will be coded using the Medical Dictionary for Regulatory Activities (MedDRA) Version 24.1 (or higher if a new version is issued during the study; see the DMP for more details). All AEs will be assigned a severity grade using Common Terminology Criteria for Adverse Events (CTCAE) Version 5.0 (or higher if a new version is issued during the study; see the protocol for more details).

A treatment-emergent adverse event (TEAE) will be defined as an AE that starts during or after the first dose, or starts prior to the first dose and increases in severity after the first dose.

A treatment-related TEAE will be defined as a TEAE with a relationship of related to the study treatment, as determined by the investigator.

All AEs will be listed. In addition to the data recorded in the database, the listings will include derived onset time and duration. Onset time will be calculated from the time of the last associated dose for TEAEs only.

The frequency of subjects with TEAEs and the number of TEAEs will be summarized for the following categories:

- TEAEs (overall, serious, leading to discontinuation, and leading to death) by treatment
- TEAEs by severity and treatment
- Treatment-related TEAEs (overall, serious, leading to discontinuation, and leading to death) by treatment
- Treatment-related TEAEs by severity and treatment

The frequency of subjects will be summarized separately for TEAEs and treatment-related TEAEs by the following:

- System organ class, preferred term, and treatment
- Preferred term and treatment

For the AE data the following rules will apply:

- For the derivation of treatment-emergent status (applicable to all AEs): If the start date/time of an AE is incomplete or missing, an AE will be assumed to be a TEAE, unless the incomplete start date/time or the end date/time indicates an AE started prior to the first dose.
- For the derivation of treatment-related status (applicable to TEAEs only): If the study treatment relationship for a TEAE is missing, that TEAE will be counted under the 'missing' category.
- For the derivation of onset time (applicable to TEAEs only): If the start date/time of a TEAE is missing, onset time will not be calculated. If the start date/time of a TEAE is incomplete, where possible, the minimum possible onset time will be calculated and presented in ' \geq DD:HH:MM' format (eg, if the date/time of the last associated dose is 01MAY2019/08:00 and recorded start date/time of a TEAE is 03MAY2019, then the minimum possible onset time will be calculated by assuming a TEAE started at the first hour and minute of 03MAY2019 [03MAY2019/00:00], thus will be presented as onset time \geq 01:16:00 in the listing). If the start date of a TEAE is the same as the date of the last associated dose but the start time of a TEAE is missing, an onset time will be presented as ' \geq 00:00:01'. Any clock changes will be accounted for in the derivation.
- For the derivation of duration (applicable to all AEs): If the end date/time of an AE is missing, duration will not be calculated. If the start or end date/time of an AE is incomplete, where possible, the maximum possible duration will be calculated and presented in ' \leq DD:HH:MM' format (eg, if the start of an AE date/time is 01MAY2019/08:00 and its recorded end date/time is 03MAY2019, then the maximum possible duration will be calculated by assuming an AE ended at the last hour and minute of 03MAY2019 [03MAY2019/23:59], thus will be presented as duration \leq 02:15:59 in the listing). Any clock changes will be accounted for in the derivation.
- For the calculation of TEAE summary statistics: If the severity of a TEAE is missing, that TEAE will be counted under the 'missing' category.
- For the calculation of TEAE summary statistics: If a subject experienced multiple TEAEs with the same preferred term for the same treatment, this will be counted as 1 TEAE for that treatment under the maximum severity recorded.

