8.4. Safety Analysis

All safety assessments, including AEs, SAEs, vital sign measurements, clinical laboratory results, physical examination results, concomitant medications, and 12-lead ECGs, will be tabulated and summarized where possible, using descriptive methodology, as needed, by timepoint. Unless otherwise specified, baseline value is defined as the last non-missing measurement before administration of study drug for each period (ie, Day 1 and Day 8). No formal statistical analyses are planned for the safety data. All safety data will be listed by subject.

Concomitant medications will be coded using the World Health Organization (WHO) Drug Dictionary (WHO Drug Global B3, September 2019). Adverse events will be coded using Medical Dictionary for Regulatory Activities Version 22.1 (or higher). The incidence of AEs will be presented by severity and by relationship to study drug as determined by the Investigator or designee ([Appendix 1](#) for AE reporting). All TEAEs will be summarized by system organ class and preferred term.

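### The repeat-event rule in SAP 8.6.1 is not limited to subject counts, so the number of TEAEs would count subject-by-term-by-treatment combinations instead of events

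*SAP*

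**What the plan says.** SAP 8.6.1 names two statistics for its main TEAE summaries: "The frequency of subjects with TEAEs and the number of TEAEs will be summarized for the following categories". The categories include "TEAEs (overall, serious, leading to discontinuation, and leading to death) by treatment" and "TEAEs by severity and treatment", each with a counterpart for treatment-related TEAEs. The tables by system organ class and preferred term are different, because they report subjects only: "The frequency of subjects will be summarized separately for TEAEs and treatment-related TEAEs by the following".

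The data rules at the end of the section then deal with repeats. The condition is "For the calculation of TEAE summary statistics: If a subject experienced multiple TEAEs with the same preferred term for the same treatment", and the consequence is "this will be counted as 1 TEAE for that treatment under the maximum severity recorded".

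The same section states that "All AEs will be listed". Protocol 8.4 has no rule for repeats. It says that "The incidence of AEs will be presented by severity and by relationship to study drug as determined by the Investigator or designee".

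**The concern.** Keeping one record per subject and term at the highest grade is a sound rule for counting subjects. It is not a rule for counting events. The SAP states it for TEAE summary statistics without restriction, so it also reaches the entries that are meant to give the number of TEAEs. Those entries would carry a label that does not describe what they hold.

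Safety and tolerability of the two tablet lots is the secondary objective, and SAP 8.6.6 plans no inferential safety analysis. The descriptive tables are therefore the main summary of the safety comparison. A table reader who takes the number of TEAEs at face value would not see recurrences, and in the severity table would not see the lower-grade ones.

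**Working it through.** The documents state no AE figure for this trial, so there is nothing to reproduce. The check is to set the provisions side by side, apply the rule to a small example, and see what its size depends on.

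**1. Where an event count is due, and what the rule does there (SAP 8.6.1)**

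| Output | Statistic promised | Effect of the rule |
|---|---|---|
| Overall, serious, discontinuation and death categories, by treatment | Subjects and TEAEs | Repeats leave the TEAE count |
| Severity, by treatment | Subjects and TEAEs | Repeats leave the TEAE count; only the highest grade is kept |
| System organ class and preferred term, by treatment | Subjects only | None: a subject already counts once per term |
| AE listings | Every AE | None |

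**2. Scope of the rule.** Three features of the text point the same way.
- The unit is one TEAE, not one subject.
- The tables by preferred term report subjects only, so they do not need the rule.
- The overall and severity summaries are not described as broken down by preferred term. A rule keyed to preferred term does not place a subject in a single severity row: Grade 1 headache with Grade 2 nausea still falls in two rows.

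No other place in the documents limits the rule or defines the number of TEAEs as every event.

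**3. The rule applied to an invented list.** Each line item is taken as a separate episode.
- Subject 1 on T: headache Grade 1, Grade 1, Grade 2. On R: headache Grade 1.
- Subject 2 on T: petechiae Grade 1 twice, nausea Grade 1.

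| | Every event | SAP rule |
|---|---|---|
| T, total | 6 | 3 |
| T, Grade 1 | 5 | 2 |
| T, Grade 2 | 1 | 1 |
| R, total | 1 | 1 |
| Subjects with any TEAE, T / R | 2 / 1 | 2 / 1 |

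The total number of subjects with a TEAE is the same either way. The headache on T and the headache on R are still counted once each.

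**4. What the size depends on.** Let r be the share of TEAEs that repeat an earlier one in the same subject, term and treatment. The table then shows a share 1 − r of events. In the example, T has r = 3/6, so half are shown. The rule can never raise a count, and it changes nothing when r = 0.

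The documents do not give r. As an assumption, let events of one term follow a Poisson distribution with mean λ per subject and treatment. The expected reported count is 1 − e^(−λ) and the expected true count is λ, so the share shown is (1 − e^(−λ))/λ.

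| Assumed λ | 0.05 | 0.1 | 0.25 | 0.5 | 1.0 |
|---|---|---|---|---|---|
| Share shown | 97.5% | 95.2% | 88.5% | 78.7% | 63.2% |

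**The case against.** The best defence is that the rule is a definition fixed in advance. It says openly how repeats are counted, and protocol 8.4 promises incidence, not a raw number of events. This stands to the extent that no protocol commitment is broken, and a sponsor may choose a collapsed count. It does not settle the matter, because the SAP itself lists the number of TEAEs as a second quantity beside the frequency of subjects. If the collapsed count is intended, the label should say so.

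SAP section 1 places the detailed description of the outputs in a separate shells document. A footnote there may already restrict the rule. That document is not available here, so the point concerns the SAP as written.

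The effect may also be slight. Protocol Table 2 shows 10 treatment-related headaches. Protocol Table 1 gives an enrollment of 10 + 20 + 9 + 24 + 15 + 27 + 16 + 16 + 16 + 31 + 16 = 200 without the hepatic impairment study. That is 10/200 = 0.05 per subject. At λ = 0.05 in 28 subjects, the expected loss is 28 × (0.05 − 0.0488) ≈ 0.03 headaches per treatment. The figure is rough: Table 2 covers related events only, does not say whether it counts subjects or events, and pools single-dose with multiple-dose studies, while the Poisson model ignores clustering within a subject. It does weigh against assuming a large effect.

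A reader might infer that event counts will be understated by a substantial share, such as 10% to 30%. The documents do not support this. They give no repeat rate, and the high rank of headache in Table 2 says nothing about recurrence within one subject.

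A reader might also infer that safety information is lost, or that a table total must match the listing. Neither follows. Every AE is listed, with onset time and duration for TEAEs, so recurrences can be counted by hand in a trial of this size. The listings also hold AEs that began before dosing, so they need not equal a TEAE table line for line.

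**Conclusion.** The concern holds as a mismatch between a counting rule and the label of the number it produces. As SAP 8.6.1 is written, the number-of-TEAEs entries, overall and by severity, for all and for treatment-related TEAEs, would count distinct combinations of subject, preferred term and treatment. They understate events whenever a term recurs in a subject on one treatment, with lower grades losing most.

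The size is unknown and may be small or zero with up to 28 subjects and one dose per period. The conclusion rests on a literal reading of the SAP and on the shells document not already restricting the rule. Subject frequencies are not in question: taking the highest grade is proper for them. The system organ class and preferred term tables, the AE listings and the PK analysis are not affected.

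**What to change.** In SAP 8.6.1, limit the rule to subject frequencies and define the event count separately. Suggested wording: *In entries that count subjects, a subject with several TEAEs of one preferred term on one treatment contributes once, at the highest grade. In entries that count TEAEs, each distinct episode contributes once, at its own grade; an episode held in several rows because its grade changed contributes once, at its highest grade.*

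The clause on grade changes is needed because the documents do not say whether a change of grade within one episode opens a new AE record. If it does, counting every row would inflate the number.

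If the collapsed count is what the sponsor wants, keep the rule and relabel those entries as subject-by-preferred-term counts.

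No new data are needed and subject frequencies stay as planned. The cost is a short SAP edit, the matching shell footnote, and minor programming to identify distinct episodes. SAP section 1 requires the SAP and shells to be final before programming starts, which is when the change is cheapest.

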8.6.2. Clinical Laboratory Parameters

All clinical laboratory parameters and their changes from baseline, will be listed, as applicable; any value outside the clinical reference range will be flagged, and whether the out of range value was deemed clinically significant or not clinically significant will be indicated. Separate listings will be provided for any parameter for which there is any individual subject value outside the respective clinical reference range.

Summary tables by treatment and timepoint will be provided for clinical chemistry, hematology, and coagulation parameters, and their changes from baseline, as applicable.

Values recorded as $< x$, $\leq x$, $> x$, or $\geq x$ will be displayed in the listings as recorded. For the derivation of listing flags, all calculations, and presentation in the figures, $< x$, $\leq x$, $> x$ and $\geq x$ values will be set to x i.e. will be considered equal to the lower or upper limit of quantification, respectively.

8.6.3. Vital Signs Parameters

All vital signs parameters and their changes from baseline, will be listed, as applicable; any value outside the clinical reference range will be flagged, and whether the out of range value was deemed clinically significant or not clinically significant will be indicated.

Summary tables by treatment and timepoint will be provided for oxygen saturation, respiratory rate, oral body temperature, systolic blood pressure, diastolic blood pressure, and pulse rate, and their changes from baseline, as applicable.

8.6.4. 12-lead Electrocardiogram Parameters

All 12-lead ECG parameters will be listed; any value outside the clinical reference range will be flagged, and whether the out of range value was deemed clinically significant or not clinically significant will be indicated.

Summary tables by treatment and timepoint will be provided for all 12-lead ECG parameters. QT interval corrected for heart rate using Fridericia's formula (QTcF) values that are > 450 msec and increase from baseline > 30 msec will be flagged in the data listing.

8.6.5. Other Assessments

Medical history and physical examination will be listed. Medical history will not be coded per MedDRA, and will be presented as reported (verbatim) on the eCRFs. Any physical examination abnormalities reported will also be flagged as clinically significant or not clinically significant as indicated.

All other safety and tolerability assessments not detailed in the above sections will be listed only.

8.6.6. Safety and Tolerability Statistical Methodology

No inferential statistical analyses are planned.

9. INTERIM ANALYSES

No interim analyses are planned.

10. SIGNIFICANT CHANGES FROM THE PROTOCOL-SPECIFIED ANALYSES

There were no significant changes from the protocol-specified analyses.

12. APPENDICES

Appendix 1: Document History

Status and Version	Date of Change	Summary/Reason for Changes
Final Version 1.0	NA	NA; the first version.

NA = not applicable
